2. OVERALL SYNOPSIS OF THE CLINICAL INVESTIGATION

[figure not shown]
Clinical investigation title:	SpO ₂ Data Collection in Pediatric Patients using INVSENSOR00061
Study objective(s):	The objective of this clinical study is to collect data to evaluate the form, fit, and function of INVSENSOR00061.
Investigational device(s):	Masimo INVSENSOR00061
Number of subjects:	Approximately 30 subjects.
Inclusion criteria:	
• Subject is a full-term newborn (37 weeks) to 18 months of age.
Exclusion criteria:	
• Subject has underdeveloped skin.• Subject has a skin condition and/or deformity at the planned application site, which would preclude sensor placement and measurements.• Subject has an absence or deformities of limbs or severe edema, which would interfere with sensor application or prevent the proper fit of the sensors.• Subject is not suitable for the investigation at the discretion of the Investigator.
Duration of the clinical investigation:	The expected duration of study enrollment is 1 to 3 months. The study devices will be worn for approximately 30 minutes by each subject.
Study endpoint(s):	Evaluate the form, fit, and function of the INVSENSOR00061.

3. IDENTIFICATION AND DESCRIPTION OF THE INVESTIGATIONAL DEVICE

INVSENSOR00061 is designed to provide parents with access to hospital-grade, clinically proven vitals monitoring technologies, such as Masimo SET®, at home. It is a modified version of the FDA-cleared RD SET® neonatal pulse oximeter sensors which measure temperature and SpO₂. The technology of the sensor is similar to the FDA-cleared neonatal sensors but differs in form and fit. The INVSENSOR00061 pulse oximeter sensor is inserted into a silicon bootie holder (Figure 1), that can be worn on either foot, which minimizes sensor slip-off that can result in false alarms. INVSENSOR00061 offers continuous monitoring of blood oxygen

level (SpO₂), respiration rate from the pleth (RRp[®]), pulse rate (PR), and temperature.

A.

B.

Figure 1. Overview of INVSENSOR00061. **A.** The INVSENSOR00061 used with a bootie that can be worn on either foot, which minimizes sensor slip-off that can result in false alarms. Considering the baby's sensitive skin, the bootie is made from soft silicone material with fabric straps, which is designed for the baby's comfort. **B.** INVSENSOR00061 placement on

4. JUSTIFICATION FOR CLINICAL INVESTIGATION DESIGN PLAN

Masimo Corporation develops noninvasive medical technologies such as Masimo Signal Extraction Technology (SET[®]), which is incorporated in Masimo SET[®] pulse oximeters and adhesive sensors. Masimo SET[®] signal processing is designed to overcome limitations of conventional pulse oximetry technologies distinguishing between pulsating blood in arterial and venous blood at the measurement site. Masimo SET[®] pulse oximeters have been FDA-cleared for the monitoring of the oxygen saturation of blood (SpO₂), pulse rate (PR), and Respiratory Rate from the Pleth (RRp) in motion and non-motion conditions. Masimo SET[®] pulse oximeters use advanced signal processing algorithms to filter out noise, such as moving venous signals, to help improve the detection of the true arterial oxygen saturation(1).

Blood oxygen saturation level represents the ratio between oxyhemoglobin (oxygenated) and deoxyhemoglobin (non-oxygenated) present in the blood. The pulse oximeter works by measuring frequencies of light, which correspond to the type of hemoglobin present in the blood. By isolating the pulsatile signal, the oxygen saturation of arterial hemoglobin can be estimated.

According to the Centers for Disease Control and Prevention (CDC), in 2020, approximately 3,400 infants died unexpectedly in the United States(3). The three common reasons were Sudden Infant Death Syndrome (SIDS), unknown cause, and accidental suffocation and strangulation in bed, which accounted for 41%, 32%, and 27% of cases, respectively(4). This makes “crib death” (another name used to refer to SIDS) the leading cause of unexpected deaths among infants less than one year old. Masimo INVSENSOR00061 aims to bridge this gap as a continuous monitor of blood oxygen level, respiratory rate, pulse rate, and body temperature. The objective of this study is to evaluate the form, fit, and function of INVSENSOR00061 when used on newborn and infant subjects. Additionally, this data will also be used to provide pilot study estimates of various statistical parameters needed for a future validation study.

To evaluate the form, fit, and function, the study will look to collect data on the application, fit, and ability to obtain the supported parameters on the intended study population. To confirm the acceptability of the form, fit, and function for each subject a standard of care FDA cleared RD SET adhesive sensor will be applied to each subject as a reference for good form, fit, and function. The standard of care sensor is provided as reference in the study because it is possible that a very small population of subjects may have physiologies that may make the supported parameters difficult to obtain.

5. BENEFITS AND RISKS OF THE STUDY DEVICES, CLINICAL PROCEDURE, AND CLINICAL INVESTIGATION**5.1. Anticipated Clinical Benefits**

There is no direct benefit to the individual for their participation in this research study. Possible future benefits would be to society as a whole. Development of new technology could enable healthcare workers to recognize and treat potentially life-threatening conditions more appropriately.

5.2. Risks Associated with Participation in the Clinical Investigation

The noninvasive devices used in this study are similar in technology and design to commercially available pulse oximeters and other noninvasive devices and hence have the same risks. Pulse oximeters and other noninvasive devices are commonly used and are considered to be minimal risk.

There is a small risk of damage to the subject's foot from the device, including temporary skin irritation, skin inflammation, itching skin, or discomfort associated with exposure to the sensor, as well as potential temporary mechanical irritation or discomfort. If there are any cuts and/or abrasions near the foot, sensors may not be placed on the particular foot to avoid any discomfort for the subjects.

The sensors have been subjected to performance, mechanical, and electrical testing, skin surface temperature and results demonstrate that the sensors meet the requirements for safety and effectiveness for intended use of the product, refer to investigational brochure for further details.

6. OBJECTIVES OF THE CLINICAL INVESTIGATION

The objective of this study is to evaluate the form, fit, and function of INVSENSOR00061.

7. DESIGN OF THE CLINICAL INVESTIGATION**7.1. General**

This is a data collection study using INVSENSOR00061 in the neonatal population. INVSENSOR00061 comes with [REDACTED] different sizes of booties that can be secured to either foot of the subject. The appropriate size bootie can be determined by following the manufacturer's *Direction for Use (DFU)* referenced in the *Investigator Brochure (IB)*. The confirmation of the form, fit, and function will be assessed based upon ability to obtain readings for the supported parameters after application on the foot. A reference standard of care FDA cleared Masimo RD SET adhesive sensor will also be applied as a reference measurement.

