7.6.4. Data Collection Procedure

7.6.4.1. A Masimo RD SET® neonatal sensor will be placed on the subject's foot, depending on subject's weight, following manufacturer's DFU and the study's procedure manual. Continuous data from the pulse oximeter will be collected from the Masimo Radical-7 (or comparable) with the Masimo Root Monitoring System.

7.6.4.2. Prior to the placement of INVSENSOR00061, the subject will be observed for crying, restlessness, etc., for approximately [REDACTED] Observations will be recorded on the case report form (CRF).

7.6.4.3. After approximately [REDACTED] INVSENSOR00061 will be placed on the opposite foot of the Masimo RD SET® neonatal sensor.

7.6.4.4. An ambient shield(s) will be used to reduce optical interference between sensors.

7.6.4.5. The Masimo RAM® sensor, if used, will be placed on the subject's chest to measure continuous respiration rate.

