7.6.4.6. The subject will then be observed for approximately [REDACTED]

7.6.4.7. After five minutes of observation, INVSENSOR00061 will be paired via Bluetooth connection to Masimo data collection software on a laptop or phone. Upon successful Bluetooth pairing of the investigational device, data collection will be initiated on the data collection software and data will be obtained continuously (SpO₂, PR, RR_p, temperature, etc.).

7.6.4.8. Data will be collected for approximately [REDACTED] using the data collection software.

7.6.4.9. During this timeframe, the subject's temperature, and manual respiratory rate count for [REDACTED] if required, may be recorded approximately every five minutes.

7.6.4.10. Sensor placement locations, sensor ID/lot number, subject's reaction prior to and after sensors placement, observations during data collection, and other relevant information will be recorded in the CRF.

7.6.4.11. The subject's parent or legal guardian will be asked to complete a survey about their observations and experiences with the device. See Sample survey in Appendix A.

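### Does the plan need a defined valid reading and a stated rule for the RD SET reference before it can judge form, fit and function?

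*Combined protocol and SAP*

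**What the plan says.** The only stated criterion is in section 7.1: "confirmation of the form, fit, and function will be assessed based upon ability to obtain readings for the supported parameters". Section 3 lists the supported parameters as SpO2, respiration rate from the pleth, pulse rate and temperature. The endpoint in the synopsis repeats the objective.

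The RD SET sensor has two descriptions. Section 4 applies it "To confirm the acceptability of the form, fit, and function for each subject", on the ground that "a very small population of subjects may have physiologies that may make the supported parameters difficult to obtain". Section 7.1 says that it "will also be applied as a reference measurement".

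On data capture, 7.6.4.1 has RD SET recorded continuously through the Radical-7 and Root, and 7.6.4.3 puts the new sensor on the other foot. Under 7.6.4.7, "Upon successful Bluetooth pairing of the investigational device, data collection will be initiated on the data collection software", and those data are also continuous. Temperature and a manual respiratory count are permissive in 7.6.4.9: "if required, may be recorded approximately every five minutes".

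Three other places bear on how much reading is expected and what it is for. Section 7.5.4 calls a subject completed at about 15 minutes of data. Section 7.3 ends the study when 30 subjects have contributed data that can be used. Section 4 says that "this data will also be used to provide pilot study estimates of various statistical parameters needed for a future validation study".

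**The concern.** Read strictly, the section 7.1 criterion is met by a sensor that reads now and then as well as by one that reads throughout. It does not say which of the four parameters must read, for how long, or in how many infants. Section 4 gives RD SET the task of separating a device that does not work from an infant who is hard to read, but no section says what follows when one sensor reads and the other does not, or when neither does. Section 8 would be the natural place, and it names no endpoint variable, summary or comparison. Redaction does not explain this: section 8 shows no redaction marks, and those in 7.6.4 fall where durations would stand.

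At stake would be the meaning of the main result. The same recordings could yield different success rates depending on a definition chosen after the data are seen. The pilot estimates meant for a later validation study are also unnamed.

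**Working it through.** **Is there a figure to reproduce?** No. The plan gives no success rate, threshold, interval or acceptance limit for function. The target of 30 rests on exceeding 15 and on a sponsor calculation that is not shown, so it cannot be re-derived. The numbers below are illustrations with assumed failure counts and exact (Clopper-Pearson) 95% intervals.

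**1. How much could the unstated RD SET rule move the result?** Assume the new sensor fails in 3 of 30 infants.

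| Assumed RD SET result in those 3 | Summary | Estimate | 95% CI |
|---|---|---|---|
| Any | Success, all infants | 27/30 = 90.0% | 73.5% to 97.9% |
| Fails in 2 | Success, infants readable by RD SET | 27/28 = 96.4% | 81.7% to 99.9% |
| Reads in all 3 | Failure specific to new sensor | 3/30 = 10.0% | 2.1% to 26.5% |
| Fails in all 3 | Same, all infants as denominator | 0/30 = 0% | 0% to 11.6% |
| Fails in all 3 | Same, infants readable by RD SET | 0/27 = 0% | 0% to 12.8% |

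For zero events the upper limit is 1 − 0.025^(1/n): 1 − 0.025^(1/30) = 0.116 and 1 − 0.025^(1/27) = 0.128.

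The first two rows use the same data and differ by 96.4 − 90.0 = 6.4 percentage points, well inside either interval. The third and fourth rows differ because the data differ: RD SET read in one case and not in the other. The planned recordings would show which case had occurred. The assumed counts are also high, since 2 or 3 of 30 infants unreadable by RD SET is 7% or 10%, whereas section 4 expects such infants to be very few.

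**2. Could an intermittent sensor pass?** Suppose any single valid minute counts, valid minutes average 20%, and there are 15 one-minute windows (15 from section 7.5.4, because the recording length is redacted). The share of infants passing is 1 − 0.8^15 = 96.5% if minutes are independent, 50% in a beta-binomial model with within-infant correlation 0.5, and 20% at correlation 1, where nothing is distorted. This depends on reading the criterion as a single reading. Sections 7.3 and 7.5.4, with their reference to usable data and to about 15 minutes of it, count against that reading. The 20% has no basis in the documents.

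**3. Can the comparison be made from what is collected?**
- Both sensors are recorded continuously in the same infant, so the share of the record with readings can be computed for each sensor, at least for SpO2 and pulse rate.
- Infants can then be sorted into four groups: both read, new sensor only, RD SET only, neither. This is the comparison that section 4 motivates.
- An infant whose sensor never pairs has no recording from the new sensor, but section 9.3 requires a CRF for every enrolled subject, including those who do not complete.
- Poor reliability or performance falls under the device-deficiency definition in 15.1 and must be recorded under 15.4. Section 7.6.4.10 adds observations during recording, and 7.6.4.11 adds a parent survey.
- Where no reference temperature or manual respiratory count was taken, availability of readings can still be described, and that is all the section 7.1 criterion asks.

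**4. Are the pilot estimates without a source?** No. Section 4 ties them to this study's data, and 7.6.4 describes the recordings. Only the parameters and method are unnamed. Section 8 mentions Arms only as a reason for the number of subjects, so it is not a planned analysis left undescribed.

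**The case for a change.** The strongest case for a change is that even a descriptive study should say what it will describe. Section 7.1 speaks of confirmation, RD SET is given a per-infant role, and neither has a rule, so the definition could be chosen after the data are seen. Writing it down would cost little, because the data are already to be collected. There is also a denominator risk. If the data required for completion in 7.5.4 and 7.3 mean readings from the new sensor (an assumption), infants in whom it fails could be replaced and drop out of the count.

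The first part stands as a remark on documentation: a sentence in section 8 would be tidier. It does not show that following the plan leads to a wrong conclusion. The main freedom left is which denominator to report, and a per-infant table shows both.

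The denominator risk is weaker than it looks. Failure to read is not in itself among the reasons for withdrawal in 7.5.4. Enrolled and completed are separate classes, and non-completers still have CRFs, so such infants remain countable.

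Further proposals, such as bias and Arms against RD SET, intervals that resample infants, or a mean paired difference, would add analyses. They would not correct one that the plan gets wrong.

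**Conclusion.** The gap is real and narrow: no section defines a valid reading or states how the RD SET result enters the per-infant judgement. No change is called for. This is missing detail in a descriptive study of about 30 infants with no hypothesis test, and an analyst can fill it sensibly from section 4 and the paired continuous recordings.

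On the same assumed data, the choice of denominator moves the success rate from 90.0% to 96.4%, with 95% intervals of 73.5% to 97.9% and 81.7% to 99.9%. The assumptions are 3 failures in 30 on the new sensor, 2 of them shared with RD SET; the documents give no rate of either kind.

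The conclusion rests on two conditions: that the report shows results for both sensors by infant, as the rationale in section 4 implies, and that enrolled infants without usable recordings are accounted for from their CRFs. The study procedure manual and the parent survey were not available for this check and may supply some of the detail.

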7.2. Investigation Site(s)

This study will be completed [REDACTED]

7.3. Definition of Completion of the Clinical Investigation

The study will be considered complete after usable data from 30 subjects has been collected and evaluated and a final clinical study report is complete, excluding those who have been withdrawn.

7.4. Study Device(s) and Comparator(s)

Investigational device:

INVSENSOR00061

- A modified version of the FDA-cleared RD SET® neonatal pulse oximeter sensors for measuring SpO₂.
- Contains the same technology as the FDA-cleared neonatal sensors but differs in form and fit. The pulse oximeter sensor is designed to be held using a holder in the form of a bootie that can be worn in either foot, which minimizes sensor slip-off that can result in false alarms.

- Considering the potential for a baby's sensitive skin, the bootie is made from soft silicone material with fabric straps.

Comparators/FDA-cleared References:

- Masimo RD SET® neonatal sensor
- Masimo Radical-7 Pulse CO-Oximeter (or comparable)
- Masimo Root Patient Monitoring System
- FDA-cleared temperature devices (Optional)
- Masimo RAM® sensor (Optional)

Research Equipment

- Laptop with data collection system or smartphone application

7.5. Subjects**7.5.1. Inclusion Criteria**

- Subject is a full-term newborn (37 weeks) – up to 18 months of age.

7.5.2. Exclusion Criteria

- Subject has underdeveloped skin.
- Subject has a skin condition and/or deformity at the planned application site, which would preclude sensor placement and measurements.
- Subject has an absence or deformities of limbs or severe edema, which would interfere with sensor application or prevent the proper fit of the sensors.
- Subject is not suitable for the investigation at the discretion of the investigator.

7.5.3. Number of Subjects

Approximately 30 subjects will be enrolled in the study.

7.5.4. Subject Classifications

Subjects will be classified according to the criteria below:

- Screened** – Subjects who have been approached for participation in the study and have been assessed for study eligibility, after the infant's parent(s), guardian(s), or legally authorized representative (LAR) has reviewed and signed the Informed Consent Form (ICF)
- Enrolled** – Subjects who have met all the inclusion criteria, do not meet any exclusion criteria, signed the ICF and have been assigned a subject identification number.
- Screen Failure** – Subjects who do not meet all the screening eligibility criteria (Reason for the subject's ineligibility will be documented on a *Screening and Enrollment Log*).
- Withdrawn** – Subjects who do not complete the study due to reasons listed below:
 - The infant's parent(s), guardian(s), or legally authorized representative voluntarily withdrew their consent.
 - Subject was discontinued from study at the discretion of the principal investigator (PI).
- Completed** – Subjects for whom approximately 15 minutes of data has been collected.

7.5.5. Study Duration

Subject participation in the study will be approximately 30 minutes following consent.

7.6. Study Procedures

7.6.1. Subject Recruitment and Pre-Screening

A partial waiver of HIPAA authorization will be requested for the pre-screening process of this study. The waiver will allow study staff to access the electronic medical record (EMR) to identify prospective subjects before introducing them to the study and obtaining their informed consent. With this partial waiver, subjects' protected health information (PHI) will remain confidential and will not be disclosed to other individuals. The data collected from this study will not be labeled with any personal identifiers or with a code that will be linked to identifying information.

7.6.2. Informed Consent Process

The investigator shall not enroll any subject to participate in the study or consent any subject prior to receiving IRB approval of the informed consent form.

Following identification of a potential eligible subject as defined by the inclusion and exclusion criteria, the subject's parent(s), guardian(s), or legally authorized representative will be approached by the study staff. The study research staff will explain the purpose and procedures of the study, risks and benefits, clarify subject's rights and privacy, and allow ample time for participating in the study. The research team will emphasize that participation is voluntary, has no monetary compensation, and declining the participation will not result in any penalty or loss of benefits that the subject is otherwise entitled.

The investigator(s) and/or staff delegated for informed consent will be responsible for conducting the informed consent process and obtaining the ICF and HIPAA/data authorization form. Informed consent is to be obtained using a form approved by the local IRB and sponsor in accordance with federal and local regulations.

The ICF and the HIPAA/data authorization forms must be signed and dated prior to conducting any study procedures. Informed consent may be obtained either in-person during the subject's pre-operative visit or remotely via phone/videoconference using an electronic form (Adobe sign, DocuSign, REDCap, etc.) as approved by the local IRB and sponsor. If the informed consent is to be conducted remotely, delegated staff will schedule a separate meeting with the subject after the subject is deemed eligible from the screening process. Subjects will be given adequate time to ask questions regarding the study and to discuss with their caregiver, family, and/or friends before making any decisions. Subjects will be informed of the risks and benefits of participating in the study and that their participation is voluntary. After all questions have been resolved, the infant's parent(s), guardian(s), or legally authorized representative may sign the ICF and HIPAA/data authorization form. Both the ICF and HIPAA/data authorization form must be signed in order for the infant to participate in the study. Parent(s), guardian(s), or legally authorized representative may withdraw their infant at any point during the study.

All signed ICF and HIPAA/data authorization forms will be kept with confidential, study-related subject documents in a locked, secure cabinet onsite and accessible only to the research team. A copy of the signed ICF and HIPAA/data authorization form will be provided to the subject.

